6.2. Whoa Baby Phase 2 Randomization

A total of 150 participants will be randomized to one of two groups in Phase 2. A randomization schedule will be created and the study coordinator will ensure that each enrollee is put into the correct group. In addition to participant randomization, bottle size preparation order will also be randomized. At the visit, participants will receive a slip of paper revealing the order in which to prepare each bottle. A biostatistician will create the randomized sequences and each participant will be asked to prepare the bottles as dictated by the sequence provided to them.

6.3. Data Analysis Plan

To address the primary aim, dry formula weights will be compared to package recommendations (i.e. 8.7 g per scoop) and classified as under-scooped, accurate scoop, or over-scooped. The proportion of bottles that are over-scooped will be compared between the two groups. Both univariate and multivariate analyses will be employed. 2x2 contingency tables with counts of participants over-scooping in each treatment arm will be constructed and chi-square tests used to compare raw proportions. This will be carried out separately for each bottle size. In addition, estimated probabilities of over-scooping for each group will be obtained from logistic regression models allowing for adjustments for bottle size and any other chosen covariates. Group-level odds ratios constructed from the estimated probabilities will be compared using two-sample t-tests. For all tests, statistical significance is defined as $p < \alpha$. Adjustments for multiple comparisons will be made when appropriate.

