In the proposed study we will assess the literacy and understanding of individuals to follow commercially available infant formula instructions. We will collaborate with the LA CaTS Health Literacy Core to improve the reading and comprehension of the manufacturer package instruction, and we will solicit the input of caregivers and key stakeholders to inform the development of educational intervention around infant feeding. Following modification of infant formula preparation instructions, we will conduct a randomized controlled trial that will test the efficacy of the modified instructions on infant overfeeding in comparison with the manufacturer package instructions. One hundred and fifty individuals will be asked to complete one study visit during which they will be asked to measure various serving sizes of infant formula following either the manufacturer package instructions or the modified instructions. The primary outcome variable will be powdered formula weight. We have designed qualitative and quantitative research studies to test the following specific aims.

1. **Aim 1 is to evaluate parental and caregiver literacy related to the use of commercially-available instructions for the preparation of infant formula.** *Hypothesis A: the health literacy of parents and caregivers to the instructions of commercially-available infant formula is variable. Hypothesis B: More than half of the parents and caregivers studied will not demonstrate adequate understanding of the infant formula instructions of the most commonly used infant formula in the US.*
2. **Aim 2 is to improve the accuracy and precision by which individuals’ measure powdered infant formula by increasing reading ease and clarity of preparation instructions.** *Hypothesis: Improving reading ease and adding explicit pictures that convey preparation instructions will increase the accuracy and precision of scoop weight when compared to the standard instructions given on the food label. We hypothesize that preparation instructions developed with a health literacy focus (Aim 1) will reduce the proportion of over-scooped bottles from 89% to 50%.*

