The majority of the commercially available infant formula exists in powdered form. Caregivers are required to correctly interpret the package label to accurately estimate the serving size and prepare a bottle of formula for the infant. This is particularly problematic because adults are unable to accurately measure estimate portion sizes [8, 15] and the preparation of infant formula requires an accurate estimate of not one but two parts that can impact the energy density of the meal; the powdered infant formula and the added water. Despite strict governance by the FDA on the precise formulation of infant formula [9], it is surprising that there is no consistency between products in the preparation instructions provided to consumers on the label and the measuring scoop used to prepare the required serving size. Difficulty in understanding preparation instructions together with an inaccurate estimation of portion sizes would lead to an incorrect preparation of infant formula bottle.

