2.3. Preliminary Studies

Preliminary data obtained in the Baby Bottle study points to an unintentional overfeeding of formula fed infants. From 2012-2013 we conducted the Baby Bottle study at PBRC (NCT01762631). The purpose of the baby bottle study was to validate the remote food photography method (RFPM) for estimating energy intake for formula-fed infants. To this end, we recruited 53 men and women aged 18-80 to prepare bottles of infant formula and take photographs of the bottles simultaneously for the RFPM. The subjects were self-identified as caregivers, that is an individual who had prepared a bottle of infant formula in the past year or non-caregivers. Subjects completed two visits approximately one-week apart and prepared three bottles measuring 2fl oz, 4 fl oz, 6 fl oz and 8 fl oz, such that two trials were conducted at Visit 1 and the final trial was conducted at visit 2. The gram weights recommended for each serving of infant formula is shown in **Figure 1**, alongside the mean \pm se of actual gram weights of servings prepared by the study subjects. Of the 636 bottles prepared, 607 or 95% contained significantly more infant formula powder (by weight) than what was recommended on the package label ($p<.0001$). This finding was

Figure 1. Actual vs. recommended scoop weights

evident for each bottle size which is suggested for infant feeding from birth until 12 months of age and averaged $11 \pm 0.6\%$ (range: -24 to +140%) over-scooping across all bottles. The caloric density of a standard scoop of infant formula is 20 kcal/fl oz and therefore with this unintentional over-scooping the prepared bottles of formula had a caloric density of 22 kcal/fl oz, the caloric density often prescribed to premature infants to accelerate infant growth rate [16]. While this error may appear to be marginal for a single bottle, the error was consistent across

Infant Age	% Overfed/ meal	Energy Intake Kcal/day	Overfed (kcal/d)	Overfed (kcal/wk)
Newborn	11	350	39	273
2 months	11	480	53	371
4 months	11	500	55	385
6 months	11	590	65	455

trials. We can therefore assume that the unintentional over-scooping is consistent within an individual and the overfeeding of the infant would then compound throughout the day as multiple bottles are consumed.

These data are summarized in **Table 1**. For each bottle size the additional

formula added to each bottle, would result in an almost entire day of additional energy intake per week.

[figure not shown]

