3.5.4. Focus Group Discussion

Focus group discussions will be led by a moderator who will follow a script of group discussion probes. During the focus group, participants will be asked to comment on discussion themes (e.g. attitudes towards infant feeding, current feeding practices, desired education regarding infant feeding, and recommendations to improve preparation instructions), and all responses will be audio and/or video tape-recorded and will be transcribed verbatim later. Responses will be de-identified in the transcript. Modified preparation instructions will be presented to the first focus group for discussion. The preparation instructions will be further modified based on participant feedback. Iterative focus groups will view and provide feedback on the preparation instructions modified by the previous focus group. Focus groups will continue until a satisfactory set of instructions are developed. Conducting focus groups in a stepwise fashion allow one focus group to build on the improvements recommended by another.

4. RESEARCH DESIGN: PHASE 2

Phase 2 is a randomized, controlled study to test the efficacy of the revised instructions on infant overfeeding in comparison with the instructions currently provided on the packaging (**Figure 4**). Individuals will be randomized in a 1:1 ratio to one of two groups:

1. **Group 1:** Group 1 participants will prepare infant formula following the standard infant formula preparation instructions provided by the manufacturer.
2. **Group 2:** Group 2 participants will prepare infant formula following the modified infant formula preparation instructions.

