4.5.3. Infant Formula Preparation

Participants will be asked to prepare 2 trials of 2, 4, 6, and 8 fl oz bottles of infant formula in random order. A total of 8 formula bottles will be prepared at Visit 1. For each bottle, the participant will follow their randomly assigned (Group 1 or Group 2 randomization) preparation instructions to measure the required amount of powdered formula. The participant will dispense the respective number of scoops of powdered formula into the formula bottle depending on which size bottle is being prepared. After all powdered formula is dispensed into the feeding bottle, PBRC staff will weigh the formula bottle with powdered formula only. The participant will continue following the instructions and pour water into the bottle and mix the formula. PBRC staff will weigh the formula bottle. This procedure will be repeated to assess intra- individual variability. Bottles will be weighed (to the nearest tenth of a gram) using a METTLER TOLEDO PB3001 scale, and dry formula and prepared formula weights will be recorded. Study staff who record the formula weights will be blinded to the randomization assignment and intended bottle size.

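### Does the plan need an analysis of prepared-bottle weight, given that every bottle is weighed again after water is added?

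*Combined protocol and SAP*

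**What the plan says.** All references are to the combined protocol and SAP.

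- **Outcome.** Section 1 states: "The primary outcome variable will be powdered formula weight". Aim 2 in the same section is about how accurately and precisely people measure powder. Its hypotheses concern scoop weight and a fall in over-scooped bottles from 89% to 50%.
- **Measurement.** Section 4.5.3 states: "A total of 8 formula bottles will be prepared at Visit 1". After the powder-only weighing, "The participant will continue following the instructions and pour water into the bottle and mix the formula", and the bottle is weighed again. Both results are kept: "dry formula and prepared formula weights will be recorded".
- **Analysis.** Section 6.3 opens by referring to the primary aim and says that "dry formula weights will be compared to package recommendations (i.e. 8.7 g per scoop) and classified as under-scooped, accurate scoop, or over-scooped". It then compares over-scooping between groups with chi-square tests and logistic regression. It does not mention prepared weight, and no other section gives an analysis of it.
- **Rationale.** Section 2.2 says that preparing formula requires estimating "not one but two parts that can impact the energy density of the meal; the powdered infant formula and the added water". Section 2.3 reports, for the earlier Baby Bottle study, that "the prepared bottles of formula had a caloric density of 22 kcal/fl oz", against a standard of 20. Section 4 gives the purpose of Phase 2 as to "test the efficacy of the revised instructions on infant overfeeding".

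**The concern.** The rationale treats powder and water as joint determinants of energy density and expresses the harm partly as 22 rather than 20 kcal/fl oz. The intervention is a rewritten set of preparation instructions, and participants pour the water under whichever set they were assigned. Water error is therefore a post-randomisation quantity that could differ between arms in either direction. Section 6.3 would not see such a difference: a bottle with exact powder and too little water is classed as accurate.

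The data that would show it are collected, by staff blinded to group, and then given no planned use. If the report went on to make claims about caloric density, those claims would either assume exact water in every bottle or rest on an analysis chosen after the data were seen.

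**Working it through.** **Inputs.** Standard density 20 kcal/fl oz, mean over-scooping 11%, and the daily energy intakes in Table 1 (section 2.3); 8 bottles per participant and weighing to 0.1 g (section 4.5.3); 150 participants, 75 per group (sections 6.1 and 6.2). The documents give no water-error rate, so every water error below is an assumption.

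**1. The plan's own figures.** Density from over-scooping: 20 x 1.11 = 22.2, stated as 22. This holds only if water is exact. The 11% is the mean over all bottles (range -24% to +140%), not over the over-scooped ones alone.

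Table 1 counts overfeeding as energy: 350 x 0.11 = 38.5, shown as 39 kcal/day, and 39 x 7 = 273 kcal/week for a newborn; 590 x 0.11 = 64.9, shown as 65 kcal/day, and 65 x 7 = 455 kcal/week at 6 months. No water quantity enters these figures.

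**2. Amount of data without a planned analysis.** 150 x 8 = 1,200 prepared weights at most. This counts data; it does not measure bias.

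**3. How far water could move density.** Taking final volume as proportional to water and ignoring the volume of the powder, density = 20 x (powder relative to target) / (1 + water error).

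| Assumed water error | Exact powder | 11% excess powder |
|---|---|---|
| -10% | 22.2 | 24.7 |
| -5% | 21.1 | 23.4 |
| 0 | 20.0 | 22.2 |
| +5% | 19.0 | 21.1 |
| +10% | 18.2 | 20.2 |

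An assumed 10% error could roughly cancel or double the effect of over-scooping on density. Nothing in the documents says how common such errors are, or whether they would differ between arms.

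**4. Does this touch the stated outcome?** Energy in the bottle depends on powder mass only. With 11% more of both powder and water, density is 20 x 1.11/1.11 = 20, but the bottle holds 11% more energy. With exact powder and 10% too little water, density is 22.2, but the energy is unchanged. Powder weight gives the right answer about energy in both cases.

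**5. Can the question still be answered later?** Prepared minus powder-only weight of the same bottle gives water mass, and the bottle's own weight cancels if both weights are recorded gross or both net. Assuming nominal volume, 29.57 mL per fl oz and 1 g/mL, a 5% shortfall is 0.05 x 2 x 29.57 = 3.0 g in a 2 fl oz bottle and 0.05 x 8 x 29.57 = 11.8 g in an 8 fl oz bottle, far above 0.1 g.

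Precision is adequate too. With 75 per group, an assumed two-sided 5% level without multiplicity adjustment, and 80% power, the detectable difference in participant means is (1.96 + 0.84) x sqrt(2/75) = 0.46 SD.

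**The case for a change.** The strongest case for a change is that it would be cheap. One secondary outcome, the powder-to-water ratio compared between arms with a model for repeated bottles, needs no new measurement, visit or participant. Writing it down before the data are seen would separate a planned comparison from one picked afterwards. The protocol's own argument makes water relevant, and the overfeeding wording in section 4 is broader than scoop weight.

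Part of this stands. Prepared weight has no planned analysis, and a between-arm comparison of density would be post hoc. Dry weight alone does not establish density.

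The rest does not make a defect. The density statements in sections 2.2 and 2.3 are background, and the 22 kcal/fl oz figure belongs to an earlier study. Section 1 attributes overfeeding to excess powder, and Table 1 counts it in kilocalories, which powder weight tracks. Under section 5.1 the formula is poured out and none is consumed, so the trial does not observe intake under either measure.

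A recorded variable without its own analysis is not an error; BMI in section 4.5.1 is in the same position. The ratio also has limits: it only approximates density, because powder adds volume, and section 4.5.3 does not say whether the two weights are gross or net.

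**Conclusion.** No change to the plan is needed. The gap is real but lies outside what Phase 2 sets out to show. Followed exactly as written, section 6.3 compares powder over-scooping between groups. Leaving prepared weight unanalysed does not bias that comparison or alter its power, and conclusions about powder measurement and the energy put into the bottle do not depend on water.

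The effect on density cannot be sized from the documents. The 20.2 to 24.7 kcal/fl oz range rests on assumed water errors of +10% to -10% and on ignoring powder volume. The two recorded weights allow analysts to derive water mass and describe the ratio by group, subject to both being on the same gross or net basis. Such a result would be exploratory and is sensibly labelled so. Prespecifying it would be a reasonable extra, but the stated aims do not require it.

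### Section 6.3 states the primary comparison both in bottles and in participants, with two bottles per participant at each size and no rule linking the two units

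*Combined protocol and SAP*

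**What the plan says.** All references are to the combined protocol and SAP.

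- **Section 6.3, bottles.** After each dry weight is classified against the label: "The proportion of bottles that are over-scooped will be compared between the two groups".
- **Section 6.3, participants.** Two sentences later: "2x2 contingency tables with counts of participants over-scooping in each treatment arm will be constructed and chi-square tests used to compare raw proportions". The sentence after that asks for one such table at every size, four in all.
- **Section 4.5.3, data collected.** "Participants will be asked to prepare 2 trials of 2, 4, 6, and 8 fl oz bottles of infant formula in random order". Each participant therefore has two bottles at each of four sizes, eight altogether. The reason for the repeat is given as "This procedure will be repeated to assess intra- individual variability".
- **Section 1, Aim 2.** The hypothesis is in bottles: a fall in the over-scooped proportion from 89% to 50%.
- **Section 6.1, Table 4.** The footnote defines the old and new proportions as proportions of participants. The design row is 0.8 against 0.5, 39 per group; 75 per group will be enrolled.
- **Section 2.3, pilot.** The reported rate is per bottle: "Of the 636 bottles prepared, 607 or 95% contained significantly more infant formula powder". On repeatability: "We can therefore assume that the unintentional over-scooping is consistent within an individual". No correlation or discordance rate is given.

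Section 6.3 also plans a logistic regression adjusted for bottle size. It does not state the unit of that model and mentions no within-person term.

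**The concern.** At any one size a participant has 0, 1 or 2 over-scooped bottles. The participant tables need a yes or no, and the plan does not say which applies to someone with one of two. Several rules fit the wording: either bottle over, both over, the mean of the two weights over, or the first trial only. The preceding sentence and Aim 2 would also allow bottles themselves to be counted.

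The choice has consequences. Counting bottles puts two related observations per person into a test that assumes independence. Counting participants makes the estimated effect depend on a rule that could be settled after the weights are known. The pilot does not supply a rule: its 53 people prepared 12 bottles each (53 × 12 = 636), three per size. Section 6.1 takes proportions of participants from those data without saying how the three repeats were combined.

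**Working it through.** **Inputs.** From the documents: two bottles per participant per size (4.5.3), 75 per arm, and 0.8 against 0.5 (6.1). Assumed: two-sided α = 0.05, because 6.3 gives no value; within-person correlation ρ of 0.3, 0.5 and 0.8, because no value is given; and bottle rates of 0.80 and 0.50. These rates borrow the Table 4 figures for illustration, although Table 4 itself is in participants.

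**1. The plan's own figure.** Pooled-variance formula without continuity correction, with p̄ = 0.65:

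n = [1.960·√(2·0.65·0.35) + 0.842·√(0.8·0.2 + 0.5·0.5)]² / 0.3² = (1.322 + 0.539)² / 0.09 ≈ 38.5, so 39 per group.

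The same formula gives 294, 82 and 23 for the other rows, so Table 4 is reproduced exactly. It is a calculation for one yes/no status per participant. With 75 per arm its power for 0.8 against 0.5 is 97.7%.

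**2. Tables filled with bottles.** There are 75 × 2 = 150 bottles per arm per size. The true variance of an arm's proportion is p(1−p)(1+ρ)/150, but the ordinary test uses p(1−p)/150. The true type I error is therefore 2·[1 − Φ(1.96/√(1+ρ))]:

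| ρ | 1.96/√(1+ρ) | True type I error |
|---|---|---|
| 0.3 | 1.72 | 8.6% |
| 0.5 | 1.60 | 11.0% |
| 0.8 | 1.46 | 14.4% |

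**3. Tables filled with participants.** For a bottle rate p:

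- P(both over) = p² + ρp(1−p)
- P(either over) = 2p − P(both over)
- P(one of two) = 2p(1−p)(1−ρ)

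Example at ρ = 0.3. Standard arm: both = 0.64 + 0.3·0.16 = 0.688; either = 1.6 − 0.688 = 0.912. Modified arm: both = 0.25 + 0.3·0.25 = 0.325; either = 1.0 − 0.325 = 0.675.

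| ρ | One of two, standard / modified | Either: rates (difference) | Both: rates (difference) |
|---|---|---|---|
| 0.3 | 22% / 35% | 0.912 vs 0.675 (23.7 points) | 0.688 vs 0.325 (36.3 points) |
| 0.5 | 16% / 25% | 0.880 vs 0.625 (25.5 points) | 0.720 vs 0.375 (34.5 points) |
| 0.8 | 6% / 10% | 0.832 vs 0.550 (28.2 points) | 0.768 vs 0.450 (31.8 points) |

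The two rules differ by (0.50 − 0.32)(1−ρ) = 0.18(1−ρ): 12.6 points at ρ = 0.3 and 3.6 at ρ = 0.8.

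**4. Sensitivity to the rates.** With Aim 2's own bottle rates, 0.89 and 0.50, the gap is (0.50 − 0.196)(1−ρ) = 0.304(1−ρ): about 21 points at ρ = 0.3 and 6 at ρ = 0.8. The illustration in step 3 does not exaggerate the gap.

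**5. Power with 75 per arm at the step 3 rates.** Over ρ = 0.3 to 0.8, power is 95.5% to 96.9% (either) and 98.4% to 99.6% (both). For a smaller effect, bottle rates 0.8 against 0.6 at ρ = 0.5, it is 69% (either) or 86% (both).

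**The case against.** The strongest reply is that this matters little if people repeat themselves. Section 2.3 assumes that over-scooping is consistent within an individual, which points to a high correlation. At ρ = 0.9 the difference is 0.816 − 0.525 = 29 points (either) or 0.784 − 0.475 = 31 points (both), and at ρ = 1 the rules coincide. That stands as a limit on the participant reading. It does not dispose of the point, because section 2.3 gives an assumption rather than a coefficient, section 4.5.3 repeats the bottles in order to measure variability, and a higher correlation makes the bottle reading worse.

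It can also be said that the table sentence names participants, so the inflated type I error belongs to a reading which that sentence excludes. This is fair. The figure is conditional on filling the tables with bottles, a reading kept open by the preceding sentence and by Aim 2.

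Four stronger readings are tempting, and the documents do not support them:

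- **The tables cannot be filled.** They can, once a rule is chosen. What is missing is the rule.
- **Table 4 disagrees with the endpoint.** A mismatch appears only if its participant proportions are entered as bottle rates, which is a substitution made by the reader.
- **The trial is underpowered.** At the planned effect, power is at least 95% under either participant rule.
- **The worst figures apply together.** The 35% with one of two bottles over needs ρ = 0.3, whereas the 14% type I error needs ρ = 0.8.

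**Conclusion.** The point holds as a conflict of units in the primary comparison. Bottles appear in Aim 2 and in one sentence of 6.3; participants appear in Table 4 and in the chi-square tables; nothing reconciles them.

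Under the bottle reading the ordinary chi-square test has a true type I error of about 9% to 14% at nominal 5%, for ρ from 0.3 to 0.8. Under the participant reading the estimated difference moves by about 13 points at ρ = 0.3 and 4 points at ρ = 0.8 between the either and both rules. Both sizes rest on assumed correlations, two exchangeable bottles per size, and bottle rates of 0.80 and 0.50.

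The effect estimate and the validity of the test are at stake, not the ability to detect the planned effect. The change should be made before the data are analysed.

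**What to change.** In section 6.3:

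1. For the per-size chi-square tables, define one status per participant per size. One option is to average the two dry weights at that size and classify the mean against the label weight. Each table then holds 75 participants per arm, with no one-of-two cases.
2. Keep the bottle-level comparison that Aim 2 states, but analyse it with a logistic model that accounts for repeated bottles within a participant (GEE or a random intercept), not with an ordinary chi-square on bottles.
3. State which unit is primary, in the same terms in Aim 2, 6.1 and 6.3.
4. Keep the separate trial weights for the intra-individual variability assessment.

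The cost is a few sentences in 6.3 with matching edits to Aim 2 and 6.1; no new data are needed. The downside is that the tables would describe a two-bottle mean, so the single-bottle rate must come from the clustered model or be reported descriptively. A mean can also be decided by one extreme bottle, and the pilot range in section 2.3 reached +140%.

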6. DATA MANAGEMENT

6.1. Sample Size Consideration

In the Baby Bottle study, participants were asked to prepare a randomly ordered set of liquid baby formula (2, 4, 6, or 8 fl oz). Estimated proportions of participants over-scooping dry formula for bottles containing each amount were obtained from this preliminary data. A separate power analysis for the proposed study was carried out for each formula amount with the Baby Bottle estimates used to represent expected proportion of participants over-scooping dry formula when using the manufacturer preparation instructions. To ensure a well powered study, each estimate from the Baby Bottle data was reduced by an additional 15%. The most conservative results from the power analyses are presented in **Table 4** and provide a sufficient sample size to

achieve desired power when comparing the control and experimental group proportions of over-scooping for any individual formula amount as well as across all amounts. In the proposed study, we hope to see the proportion of participants over-scooping formula reduced to 50% following use of the new preparation instructions. 75 participants will be enrolled in each study group, ensuring 80% power to detect this decrease.

Table 4. Sample size calculations¹

Power (%)	Proportion over-scooped: OLD	Proportion over-scooped: NEW	N Per Group
80	0.8	0.7	294
80	0.8	0.6	82
80	0.8	0.5	39
80	0.8	0.4	23

¹*Old Proportion* represents the proportion of participants expected to over-scoop formula when using the existing instructions. *New Proportion* represents the reduced proportion of participants that are expected to over-scoop formula when using the new instructions.

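### The logistic model adjusted for bottle size names no method for repeated bottles from one participant, and its stated test (t-tests of odds ratios) cannot test the arm effect

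*Combined protocol and SAP*

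**What the plan says.** - **Unit of randomisation (section 4, Research Design: Phase 2).** "Individuals will be randomized in a 1:1 ratio to one of two groups". Sections 6.1 and 6.2 give 150 participants, 75 per group.
- **Measurements (section 4.5.3).** Each person makes two trials of 2, 4, 6 and 8 fl oz: "A total of 8 formula bottles will be prepared at Visit 1". The reason for the second trial is given as "This procedure will be repeated to assess intra- individual variability".
- **Hypothesis (section 1, Aim 2).** The new instructions "will reduce the proportion of over-scooped bottles from 89% to 50" per cent, so the claim is about bottles.
- **Analysis (section 6.3).** "The proportion of bottles that are over-scooped will be compared between the two groups". Two analyses follow. The first is a set of chi-square tests, one per bottle size, on numbers of participants. In the second, "estimated probabilities of over-scooping for each group will be obtained from logistic regression models allowing for adjustments for bottle size", with other covariates possible. The inference attached to the model is: "Group-level odds ratios constructed from the estimated probabilities will be compared using two-sample t-tests".
- **Power (section 6.1).** The sample size is said to suffice "for any individual formula amount as well as across all amounts".
- **Expected correlation (section 2.3).** From the preliminary study, the authors assume that a person who over-scoops does so consistently.

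No section names generalised estimating equations (GEE), a random effect, a clustered variance or a participant-level summary. Section 6.3 mentions multivariate analyses in general, but that does not specify any of these.

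**The concern.** Bottle size varies within a person, so a model that adjusts for it must hold several rows per participant. Those rows are correlated, and the authors themselves expect this. The plan gives no way to account for it.

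The one test the plan attaches to the model is also not a test of the arm effect. A two-sample t-test needs two samples of independent values and a variance. Group-level odds ratios supply neither.

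The model is the only described analysis that combines bottle sizes, so the Aim 2 claim about bottles and the claim of power across all amounts both depend on it. An analyst who finds the t-test unworkable will probably turn to the default test of the arm term. With bottles as independent rows, that test can declare a difference between instructions that do not differ, at well above the nominal rate.

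**Working it through.** **Inputs.** From the documents: 75 per arm; 8 bottles each (4 sizes, 2 trials); rates of 0.8 and 0.5 (Table 4), 0.89 (Aim 2) and 0.95 (section 2.3). Assumed: two-sided alpha 0.05, because section 6.3 gives no number, and ICC from 0.05 to 0.7, because no within-person correlation is reported.

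**1. The plan's own figure.** The usual two-proportion formula (pooled variance under the null, two-sided 0.05, 80% power, no continuity correction), for 0.8 versus 0.5:

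n = [1.96·√(2·0.65·0.35) + 0.842·√(0.8·0.2 + 0.5·0.5)]² / 0.3² = 38.5, rounded up to 39.

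The other rows give 294, 82 and 23. All four match Table 4, which supports the assumed alpha and sidedness. The calculation takes one observation per participant.

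**2. Rows in the model.** With one trial per size there are 150 × 4 = 600 rows. With both trials there are 150 × 8 = 1,200. The plan does not say which.

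**3. The stated t-test.** Two arms yield one between-arm odds ratio, or one odds per arm. There is no replication from which to form a variance, so the procedure as written has no computable error rate. One way to force it into an executable form is to t-test the model's fitted probabilities between arms. In simulation with no arm effect (8 rows, null rate 80%, 1,500 runs per ICC), this rejected in 92% to 99% of runs, because fitted values differ only by arm and bottle size and carry no sampling error. That is one reading only.

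**4. The likely substitute: a Wald test of arm with independent rows.** With m rows per participant the design effect is 1 + (m − 1)·ICC, and

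type I error = 2·Φ(−1.96 / √(1 + (m − 1)·ICC)).

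Example, m = 8 and ICC 0.3: design effect 3.1, 1.96/1.761 = 1.113, error 26.6%.

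| ICC | 4 rows | 8 rows |
|---|---|---|
| 0.05 | 6.8% | 9.2% |
| 0.1 | 8.6% | 13.3% |
| 0.3 | 15.5% | 26.6% |
| 0.5 | 21.5% | 35.6% |
| 0.7 | 26.6% | 42.0% |

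**5. Simulation.** Beta-binomial data with no arm effect, 75 per arm, a logistic model with arm and four-level bottle size, null rates of 50%, 80%, 89% and 95%, and 4,000 replicates per setting:

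| Variance | 4 rows | 8 rows |
|---|---|---|
| Independent rows | 6.2–27.3% | 8.7–43.0% |
| Clustered on participant | 4.3–6.0% | 4.5–6.3% |

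The highest clustered values occur at the 95% null rate. A smaller separate run (8 rows, null rate 80%, 1,500 replicates) gave 12.5%, 26.5%, 35.4% and 44.4% at ICC 0.1, 0.3, 0.5 and 0.7 with independent rows. Clustered variance gave 4.7% to 5.7%.

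**6. Size-specific chi-square tests.** With one classification per participant these keep the nominal error. The plan does not say how two trials of a size become one classification. If both were entered separately, the same formula with m = 2 gives 5.6% to 13.3% over ICC 0.05 to 0.7.

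**The case against.** **The inflated error belongs to an analysis the plan does not state.** Section 6.3 never says that bottles will be independent rows or that the arm term will get a Wald test. This is correct, and the percentages in steps 4 and 5 are conditional on that choice. The fault in the t-test needs no such condition.

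**The rates are two-sided.** About half of the false rejections would favour the manufacturer's instructions. This stands too. The comparison per side is given in the verdict, and the excess remains.

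**The ICC has no numerical source.** Section 2.3 supports a positive correlation but not the upper half of the range, and the low end is modest. Any positive ICC still inflates the error.

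**A valid participant-level analysis already exists.** The chi-square tests count participants, as does Table 4. This limits the harm for each size taken alone. But those tests do not combine sizes, they lack a rule for the two trials, and the hypothesis is worded on bottles.

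**GEE is only one option.** A participant-level summary or a mixed logistic model would also handle the correlation. However, a random-intercept model targets a different quantity. For marginal rates of 0.8 and 0.5 the odds ratio is (0.8/0.2)/(0.5/0.5) = 4.0. A normal random intercept with equal spread in both arms would give 4.3, 4.6, 7.1 and 15.5 at ICC 0.05, 0.1, 0.3 and 0.5. The choice should therefore be made in advance, and section 6.3 asks for group probabilities, which are marginal.

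**Conclusion.** The concern holds in both parts. The test written for the only analysis that combines bottle sizes is invalid at any ICC. Separately, no method is named for the correlation among a participant's bottles.

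If the gap is filled with independent rows, a nominal 5% two-sided error becomes 6.8% to 26.6% (4 rows) or 9.2% to 42.0% (8 rows) at ICC 0.05 to 0.7. Halving these, false findings in favour of the new instructions run at 3.4% to 13.3% and 4.6% to 21.0%, against a nominal 2.5%. The figures rest on an assumed alpha and ICC and on that substitute analysis.

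The harm is to type I error and interval width. Sample size and power are not in question.

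**What to change.** Change the wording of section 6.3 as follows:

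1. Fit the logistic model by GEE clustered on participant, with robust standard errors and with arm and bottle size as covariates. This yields the marginal group probabilities the section asks for.
2. Base inference on that model's test of the arm effect, and delete the two-sample t-tests of odds ratios.
3. State whether both trials of each size enter the model (8 rows) or one (4 rows).
4. As a secondary clarification, state in advance how the two trials give one classification per participant in each size-specific chi-square test.

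**Cost.** No participants or measurements are added. Confidence intervals on the log odds ratio scale are wider than with independent rows by √(1 + (m − 1)·ICC): a factor of 1.07 to 1.76 with 4 rows and 1.16 to 2.43 with 8 rows at ICC 0.05 to 0.7. The robust variance may be slightly liberal when rates are near 95% (up to 6.3% in simulation).

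Power is not a barrier. In the worst case, ICC 1, each participant contributes the information of one bottle. A two-proportion z-test with 75 per arm for 0.8 versus 0.5 then has z = (0.3 − 1.96·√(2·0.65·0.35/75)) / √((0.16 + 0.25)/75) = 1.99, so power is 97.7%.
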